1.0 Project Summary/Abstract

Our long-term goal is to demonstrate the effectiveness of acupuncture for the treatment of adults with chronic pain of sickle cell disease (SCD), a debilitating pain syndrome characterized by acute and chronic pain. The objective of this study is to explore the feasibility and acceptability of acupuncture with adult sickle cell patients. We will conduct the study with adults with chronic pain from SCD, 18 years old or greater. They will all receive acupuncture. Treatments will be twice weekly for 5 weeks for 30 minutes. At baseline and post-treatment, subjects will complete measures that include pain, fatigue, anxiety, depressive symptoms, injustice experience, pain catastrophizing, and be interviewed about their feelings about receiving acupuncture. Subjects will also complete a measure of study acceptability, the Protocol Acceptability Scale for Treating SCD with Acupuncture at post-treatment. We will describe the procedures and potential challenges to implementing the acupuncture protocol and the range in the subjects' Acceptability Scale scores. We expect to identify and rectify any procedural problems subjects will report regarding the 10-session study protocol.

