3.0 Objectives/Aims

Aim: To determine the feasibility (recruitment, retention, completion) and acceptability of performing acupuncture on 15 adult subjects with SCD.

Hypothesis: Acupuncture therapy will be feasible (80% recruitment, retention, completion) and acceptable to adults with SCD.

Impact: Acupuncture therapy has the potential to significantly reduce the pain and associated symptoms of SCD by offering therapy that is complimentary to optimal medical management. Symptom management is critical for reducing disability and improving quality of life for people with SCD.

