1. What made you decide to join this study on acupuncture?
 - a. Tell me about any past experiences you had with acupuncture
 - b. Do others in your life use acupuncture?
 - c. Not satisfied with your level of pain?
 - d. Heard acupuncture is used to treat pain.
2. What were your expectations for getting acupuncture prior to participating in this study?
3. Think about your overall acupuncture experience, how would you describe your experience?
 - a. What do you think was happening in your body?
 - b. Did you learn anything from the process of getting acupuncture? What did you learn?
4. Describe how acupuncture affected your pain
 - a. Did anything change about how you think about or relate to your pain after going through acupuncture treatments?
5. Did anything about getting acupuncture surprise you?
6. How is the acupuncture healthcare experience different from other healthcare experiences you have had?
7. How did you feel about the acupuncturist?
 - a. Did the acupuncturist treat any medical issues other than pain? What was that like?
8. Tell me the reasons you would or would not continue to get acupuncture in the future.
9. Is there anything else you would like us to know about how acupuncture affected you and your overall experience?

Protocol Acceptability Scale for Treating Sickle Cell Disease with Acupuncture *

(select the most appropriate answer)

1. Was participating in this study too hard?
 Not hard at all
 Somewhat hard
 Too hard
2. Were the study instructions easy to understand?
 Easy to understand
 Somewhat hard to understand
 Too hard to understand
3. Were the study questions easy to see?
 Easy to see
 Somewhat hard to see
 Too hard to see
4. Did you feel rushed to complete this study?
 Not rushed at all
 Somewhat rushed
 Too hard to complete
5. Did you enjoy being in this study?
 Enjoyed participating
 Somewhat enjoyed participating
 Did not enjoy participating
6. What did you think of getting acupuncture?
 I liked it
 I did not like it
 I didn't like it or not like it
7. Did you think acupuncture was painful?
 It was not painful
 It was painful
8. Would you get acupuncture again?
 I would get it again
 I would not get it again
9. Do you think this study will be well received by other adults with sickle cell disease?
 Others will enjoy being in this study
 Others will somewhat enjoy being in this study
 Others will not enjoy being in this study
10. Do you think the study was:
 Too short
 Too long
 Right length

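### Acceptability Scale item 6, the only item asking whether subjects liked acupuncture, words its neutral answer like a dislike and prints it last, so neutral and dislike can be confused on the form

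*Combined protocol and SAP*

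**What the plan says.** Section 3.0 sets one aim with two parts, feasibility and acceptability, in 15 adults. The hypothesis attaches 80% to recruitment, retention and completion, and otherwise says only that acupuncture will be "acceptable to adults with SCD". It gives no cut-off for acceptability.

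Section 8.0 has the Protocol Acceptability Scale completed once, by self-report, after the last session. Section 1.0 plans to describe the "range in the subjects' Acceptability Scale scores". Sections 9.0 and 12.0 plan descriptive statistics and give no scoring rule for this scale.

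On the form itself (Appendix B):

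- Item 6 asks "What did you think of getting acupuncture". A plain positive answer is followed by "I did not like it" and then by "I didn't like it or not like it".
- Item 7 asks "Did you think acupuncture was painful" and item 8 asks "Would you get acupuncture again". Each has two clear answers.
- Item 10 begins "Do you think the study was" and offers too short, too long and right length, in that order.
- No numeric code is printed beside any answer.

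**The concern.** The third answer to item 6 can only sensibly be meant as neutral, because the first two already cover like and dislike. Its opening words are the contracted form of the dislike answer, and a second negative follows. By item 6 the subject has answered five items running from favourable to unfavourable, so the last position suggests the strongest rejection. Wording and position both point away from the intended meaning.

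The error would arise when the box is ticked. The form is given once, so recoding cannot recover what the subject meant. At stake is whether subjects who did not positively like acupuncture were indifferent or averse. That distinction matters in a study meant to inform protocol revisions for a later randomised trial (Section 2.0).

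**Working it through.** The documents give no figure on this point to reproduce. The check is a reading of the ten items, followed by simple arithmetic.

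**1. Answer order on the form**

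| Items | Options | Last printed answer |
|---|---|---|
| 1, 2, 3, 4, 5, 9 | 3 | Least favourable |
| 7, 8 | 2 | Unfavourable |
| 6 | 3 | Intended neutral, after the dislike answer |
| 10 | 3 | Most favourable (right length) |

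Eight of the ten items run from favourable to unfavourable; items 6 and 10 do not. Of the eight three-option items, six end on the least favourable answer.

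**2. Effect of misreading item 6**

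Let a be the number of neutral subjects who tick dislike and b the number of subjects who disliked acupuncture but tick neutral. With n forms:

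- shift in the dislike proportion = (a − b)/n
- shift in the neutral proportion = (b − a)/n
- shift in the liked proportion = 0, because neither error touches that box.

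With n = 15 (Section 3.0), the net shift is 1/15 = 6.7 percentage points for one answer, 2/15 = 13.3 for two and 3/15 = 20.0 for three. If only 80% of subjects reach the post-treatment form (an assumption borrowed from the completion target), n = 0.80 × 15 = 12 and one answer is worth 1/12 = 8.3 points. The documents give nothing from which to estimate a or b, so neither the size nor the sign of a − b is known. Errors in opposite directions would cancel in the proportions while individual answers stayed wrong.

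**3. Cross-checks available**

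Item 8 asks about willingness to repeat the treatment. The interview guide covers the overall experience and the reasons for continuing or not. Data are held under a code number (Section 8.0), so a doubtful item 6 answer could be compared with both. But willingness to repeat is not the same as liking: an indifferent subject may answer item 8 either way.

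**4. Item 10 and any total score**

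Too short and too long lie on opposite sides of right length, so the three answers have no single favourable-to-unfavourable order as printed. As an illustration only, *assume* answers are coded 1, 2, 3 by printed position and summed.

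- Range: minimum 10 × 1 = 10; maximum 8 × 3 + 2 × 2 = 28.
- Favourable on every item, including right length: 9 × 1 + 3 = 12. The same answers coded by meaning give 10.
- Subject R disliked acupuncture, found it painful, would not repeat it, called the study too short and was otherwise favourable: items 1–5 and 9 give 6, then 2 + 2 + 2 + 1, total 13.
- Subject N was neutral, found it not painful, would repeat it, called the length right and was otherwise favourable: 6 + 3 + 1 + 1 + 3 = 14.
- If both answer right length, R scores 6 + 2 + 2 + 2 + 3 = 15 and N stays at 14, which is the correct order.

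The reversal of R and N therefore needs both positional coding and different answers to item 10. With item 10 left out and item 6 coded by meaning, R scores 6 + 3 + 2 + 2 = 13 and N scores 6 + 2 + 1 + 1 = 10.

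**The case against.** The three answers are read together, and a subject who disliked acupuncture meets a plain dislike answer directly above the awkward one. Nothing shows that anyone would misread the item, and 6.7 points is simply one subject in 15. The study is small, uncontrolled and descriptive; no stated acceptability threshold depends on item 6; and item 8 and the interview cover nearby ground. The scale is adapted from sources that cannot be consulted here, so the wording may be inherited.

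Much of this stands. It limits the point to a risk in the neutral/dislike split. It does not make the wording clear, and the cross-checks are indirect.

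A reader might infer more than the documents support:

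- *That item 6 is the only item on subjects' opinion of acupuncture.* Items 7 and 8 also ask about it. Item 6 is the only one on liking.
- *That acceptability will be misclassified or biased in a known direction.* Errors can run both ways, and no rate is available.
- *That the Acceptability Scale score is mis-ordered.* This needs coding by printed position, which the documents nowhere state. Coded by meaning, or reported as item frequencies, the ordering error is zero.
- *That item 10 misleads subjects.* Its labels are clear; the issue is only how it would be scored.

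**Conclusion.** The point holds as a form-design weakness in one item. Item 6's neutral answer is worded almost like its negative answer and sits where a subject would expect the least favourable one, so neutral and dislike can be confused at completion. Each net misread answer is worth 6.7 percentage points of the dislike proportion at n = 15. The liked proportion is largely safe. This rests on two judgements: that the third answer is meant as neutral, and that its wording and position make misreading plausible. The frequency and direction of misreading are unknown.

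Item 10 is a secondary matter of reporting. The missing scoring key leaves the planned scores undefined, but that is missing detail rather than evidence of a wrong score.

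**What to change.** Reprint item 6 with three answers in this order: *I liked it*; *I neither liked nor disliked it*; "I did not like it". Report the three counts.

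Report item 10 as three counts (too short, right length, too long) and leave it out of any total. If a total of the remaining items is kept, add one sentence stating that every item is coded by meaning, from favourable to unfavourable.

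The cost is a few lines on one paper form, one scoring sentence and a minor form revision for the IRB. The downside is a slight departure from the source wording of a scale that has already been adapted for this study.

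If forms have already been completed (Section 9.0 is partly in the past tense), lead with the liked count, show the other two counts as printed, and tabulate them against item 8 with a note on the ambiguity.
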